4.6 Study Therapies

Bamlanivimab (LY3819253) is a neutralizing IgG1 monoclonal antibody (mAb) to the spike protein of SARS-CoV-2. It is designed to block viral attachment and entry into human cells, thus neutralizing the virus, potentially preventing and treating COVID-19.

4.7 Variables/Measures

The primary outcome of interest is COVID-related hospitalization rate in study participants and matched controls. We list all potential covariates in two phases. Phase I covers historical data and Phase II includes post COVID-19 diagnosis information. Phase I historical data will be

collected for both study participants and matched controls. Phase II post-COVID 19 diagnosis data has two parts: data elements to be collected for both study participants and matched controls (Phase II.A), and data elements to be collected for only study participants (Phase II.B).

Phase I - Historical data: Study participants and matched controls:

1. COVID-19-related information:

Variable	Data source for study participants	Data source for matched controls
Date of COVID-19 diagnosis test	ProtectWell	Optum EMR or CDSM
Type of COVID-19 diagnosis test*		
Symptomatic flag during COVID-19 test	ProtectWell (all study participants are symptomatic)	Optum EMR
Previous COVID diagnosis flag	CDSM	Optum EMR or CDSM
Previous receipt of Bamlanivimab	UHC claims	Optum EMR or UHC Claims

*: Please see Table A1 in Appendix 1 for LOINC codes of the PCR and antigen COVID-19 tests.

Commented [WWY15]: This variable won't be used for analysis.

Commented [JAT16R15]: Not necessarily. We'll use it to approximate date of symptoms onset and identify matched controls who got COVID-19 around the same time. Please see the comment below for more details.

Commented [WWY17]: Would also include COVID-19 symptoms, and a timing variable: duration since symptom onset to index date

Commented [JAT18R17]: We will include these data fields if available. Regarding date of symptoms onset, it's approximated to be 2 days prior to date of COVID-19 diagnosis (1 day for overnight shipping of COVID-19 test kit and the other day for PCR test).

2. Demographic:

Variable	Data source for study participants	Data source for matched controls
Age as of 2021*		
ZIP code of residence (may or may not be used for identifying matched controls)		
Urbanization of residence in a zip code level (urban, suburban, rural)		
Region/State of residence		
Race		
Gender		
Flag determining whether a patient resides in a nursing facility – determining a patient does not live at home		

*: Age = 2021 – birth year.

Commented [WWY19]: As obesity is a high risk factor, suggest to include BMI as a covariate in PS matching

Commented [JAT20R19]: Agreed. We include obesity as a comorbidity in 4. Comorbidities in 2019 part below. This comorbidity is extracted from our claims data.

It makes perfect sense to include BMI, but we don't have this numerical value from the claims data and have very limited coverage from other data sources.

3. Insurance:

Variable	Data source for study participants	Data source for matched controls
Line of business		
Dual-eligibility status		
Continuous member enrollment in 2019	UHC claims	Optum EMR or UHC claims
Continuous member enrollment in 2020		
Continuous member enrollment in 2021 (up to available months)		

4. Comorbidities in 2019:

Variable	Data source for study participants	Data source for matched controls
Elixhauser score for readmission	UHC claims	Optum EMR or UHC claims
Historical flag for all associated comorbidities used in computing Elixhauser score*		

*: The 29 categories include diabetes, obesity, chronic pulmonary disease, congestive heart failure, etc. The full list is in Table A2 of Appendix 1.

Commented [WWY21]: Will comorbidities be looking only in 2019?

Commented [JAT22R21]: Yes, we chose the year 2019 because the year 2020 is a special year, and people tend to use healthcare less than usual. Besides, we assume that comorbidities listed here last to the end of our study or even longer given most of them are chronic (e.g. T2D, renal failure, congestive heart failure) and our study cohort is the Medicare Advantage cohort.

5. Immunosuppressive treatment

Variable	Data source for study participants	Data source for matched controls
History of receiving immunosuppressive treatment 6 months prior to date of COVID diagnosis*	UHC claims	Optum EMR or UHC claims

*: Please see the full list of immunosuppressive prescriptions in Table A3 of Appendix 1.

Phase II.A: Post COVID-19 diagnosis data: Study participants and Matched controls

Variable	Data source for study participants	Data source for matched controls
Date of COVID-19 admission (if hospitalized)		

CONFIDENTIAL

[Protocol number: UHG (J2X-NS-I002)] SAP [\[v.3\]](#)

ER flag (admitted from ER; if data is available)		
ICU flag (related to ICU transfer; if data is available)	BCRT	Optum EMR or BCRT
Ventilation flag (use of ventilation; if data is available)		
Diagnosis code – primary		
Diagnosis code – secondary		
Diagnosis code – tertiary		
Date of discharge (if applicable)		
Date of death (if applicable)		

Phase II.B: Post COVID-19 diagnosis data: Study participants only

Variable	Data source for study participants
Infusion date	
History of adverse effects (if any)	
Details of adverse effect (if any)	Optum infusion pharmacy
Types of adverse effects (if any)	
Date of experiencing adverse effects (if applicable)	

LY3819253

5. Statistical Analyses

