6. STUDY PROCEDURES

6.1 Procedures

Optum Infusion:

Optum Infusion Pharmacy is a home infusion provider that will manage the shipment and administration of the study drug to the participants per the study protocol. Upon testing positive for COVID-19, Optum Infusion Pharmacy will be notified by the sponsor. The study drug will be shipped from a licensed pharmacy in validated cold chain containers and administered as soon as possible by registered nurses at the participant's home within 10 days of symptom onset.

Receipt of Bamlanivimab:

One-time dose of Bamlanivimab, delivered via infusion through the vein, lasting around 30 minutes

Active Participation Period (up to Day 28):

After the Optum Infusion Nurse visit has concluded (any adverse event information during and immediately post-infusion will be collected by the Nurse and will be filed for safety assessment), participant will begin ProtectWell tracking on a daily basis from Day 1 (how do you feel starting on Day 1 – this is the baseline) through Day 28 with the following approach: Day 1 rating (1-10 with 1 being the worst they can feel and 10 being the best they can feel) and then rating on a daily basis Day 2-28 (if rating remains in a 1-3 range, this will trigger clinical follow-up as the participant is not getting better).

Note: if traditional ProtectWell tracking cannot be utilized, the participant will be provided with contact information to report any issues that they are experiencing or to report that they are not feeling well.

End of Study:

Given the virtual nature of participation after the initial in-person infusion visit, participants will receive a notification on Day 28 thanking them for their participation and asking if they are willing to complete a brief survey on their study experience.

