4.4 Study Population

4.4.1 Selection Criteria

Both study participants and matched controls will meet the inclusion and exclusion criteria below.

Inclusion Criteria:

- Age 65+, confirmed SARS-CoV-2 positive, located in an area where Bamlanivimab (LY3819253) is available for infusion
- Have mild or moderate COVID-19 symptoms (after stage 1 of symptom tracking)

Commented [JAT4]: Update to keep the same criteria in the latest protocol (version 10 on Feb 3, 2021).

Commented [JAT5]: Remove it as it is no necessary for active participants and controls.

- Control only: Confirmed symptomatic COVID-19 through Optum EMR data.

Exclusion Criteria:

- Current (from first symptom report) hospitalization for COVID-19
- Prior administration of Bamlanivimab

Commented [JAT6]: Remove as not necessary per the EUA.

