6.3 Appendix 3: Mock TFLs

Tables:

Table A4. Characteristics of study participants and the pool of potential controls. For notation, n indicates the cohort size (i.e., number of subjects); IQR is interquartile range; SD is standard deviation; % indicates percentage.

Characteristics	Study participants ($n =$)	Pool of potential controls ($n =$)	p-value (study participants vs pool of potential controls)
Age: median (IQR) or mean (SD)			
Age: n (%)			
65-			
65 – 69			
70 – 74			
75 – 79			
80+*			
*: We can separate 80+ into finer groups as needed.			
Gender: n (%) in female			
Race: n (%)			
White			
Black			
Asian			
Hispanic			
Other			
Urbanization of residence: n (%)			
Urban			
Suburban			
Rural			

Commented [XM55]: Please add footnotes for each table, such as abbreviation, test for p-value, model specification and locations for:
 Dataset: dataset location/dataset name.sas7bdat
 Program: program location/program name.sas
 Output: output location/output name.rtf

Commented [XM56]: Would separate this table into two tables – before and after PS match, since there may be study participants could not find matched control

CONFIDENTIAL

[Protocol number: UHG (J2X-NS-I002)] SAP [v.3]

Socioeconomic index: median (IQR) or mean (SD)	
Dual status: n (%) With Medicaid Elixhauser comorbidity score: median (IQR) or mean (SD)	
Elixhauser conditions*: n (%) *: There are 29 conditions in total as shown in Table A1.	
Immunosuppressive treatment 6 months prior to date of COVID diagnosis: n (%)	
Stay in nursing facility during COVID test*: n (%) *: This availability depends on the claims lag. We may have partial information from the BCRT data but it's only COVID related and doesn't cover a stay of nursing facility due to other reasons.	
COVID-related hospitalization during Days 1-28 after the treatment (i.e., Bamlanivimab infusion for study participants, synthetic treatment for control candidates and matched controls): n (%)	

LY3819253

Dataset: dataset location (data table name with the corresponding database in Google BigQuery)

Program: program location/program name.R

Output: output location/output name.csv or .xlsx

Repeat Table A4:

Table A4.2

Patient demographics and other baseline characteristics

Propensity score matched population

Programming notes:

Replace “study participants” with “study participants after propensity score matching” and replace “the pool of potential controls” with “matched controls” in the header.

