Table A8. Standardized difference in mean and variance ratio of the propensity score and all matching covariates before propensity score matching

Commented [XM58]: Would report both results before and after match

Variable	Standardized difference in mean	Variance ratio
Propensity score		
Age (continuous or categorical):		
65-		
65 – 69		
70 – 74		
75 – 79		
80+*		
*: We can separate 80+ into finer groups as needed.		
Gender		
Race:		
White		
Black		

LY3819253

CONFIDENTIAL

[Protocol number: UHG (J2X-NS-I002)] SAP [\[v.3\]](#)

Asian	
Hispanic	
Other	
Urbanization of residence:	
Urban	
Suburban	
Rural	
Socioeconomic index	
Dual status	
With Medicaid	
Elixhauser comorbidity score	
Elixhauser conditions [*]	
[*] : There are 29 conditions in total as shown in Table A1.	
Immunosuppressive treatment 6 months prior to date of COVID diagnosis	

Dataset: dataset location (data table name with the corresponding database in Google BigQuery)

Program: program location/program name.R

Output: output location/output name.csv or .xlsx

Repeat Table A8:

Table A8.2

Standardized difference in means and variance ratio of the propensity score and all matching covariates after propensity score matching

Propensity score matched population

Programming notes:

Replace “before propensity score matching” with “after propensity score matching” in the table title.

LY3819253

CONFIDENTIAL

[Protocol number: UHG (J2X-NS-I002) SAP [v.3]

Table A9. Unadjusted and adjusted measures of COVID-19 hospitalization risk in study participants and matched controls.

Outcome	Results (e.g., 95% CI and p-value)
Rate of COVID-19 hospitalization w/o considering censoring on Day 28 (i.e. binary endpoint) among study participants vs matched controls	
Adjusted odds ratio w/o considering censoring on Day 28 (i.e. binary endpoint) among study participants vs matched controls	
Adjusted hazard ratio with considering censoring on Day 28 among study participants vs matched controls	

Commented [XM59]: Would include 95% CI and p value.

Commented [XM60]: Not sure what this mean?

Commented [JAT61R60]: This means a binary response. If we don't observe a covid-19 hospitalization for a patient within 28 days after his/her treatment, we define this response as 0, instead of censoring on Day 28.

Dataset: dataset location (data table name with the corresponding database in Google BigQuery)

Program: program location/program name.R

Output: output location/output name.csv or .xlsx

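### Nothing requires controls to live at home, and the planned matching and balance lists omit the nursing-facility flag although participants are infused at home

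*SAP*

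**What the plan says.** Protocol 6.1 has the drug "administered as soon as possible by registered nurses at the participant's home within 10 days of symptom onset".

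SAP 4.4.1 states that "Both study participants and matched controls will meet the inclusion and exclusion criteria below". The criteria that follow cover age, a positive test, drug availability in the area and mild or moderate symptoms. The exclusions are current COVID-19 hospitalization and "Prior administration of Bamlanivimab". The one criterion specific to controls is "Control only: Confirmed symptomatic COVID-19 through Optum EMR data". Protocol 5.3 is similar, except that its controls must have sought care at an OptumCare facility. Place of residence in the sense of home or facility appears in neither list, nor in the Table 3 definition of the control pool, nor in the control-selection text of SAP 5.8.1.2.

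SAP 4.7 introduces its variables with "We list all potential covariates in two phases" and includes, for both groups, "Flag determining whether a patient resides in a nursing facility – determining a patient does not live at home". Protocol 4.4 lists the same variable. Table A4 has a row for "Stay in nursing facility during COVID test", repeated for the matched population in A4.2. Its footnote says that availability depends on claims lag and that the inpatient census source (BCRT) gives only partial, COVID-related information.

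Table A5 (planned risk factors), Table A8 ("Standardized difference in mean and variance ratio of the propensity score and all matching covariates before propensity score matching") and Table A11 (the same for double-score matching) have no such row. SAP 5.2 does not name the flag among the outcome-model covariates.

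**The concern.** Home infusion largely determines who can be treated: people living at home. The control pool has no such restriction. A symptomatic facility resident aged 65 or over with an EMR record qualifies, and can be paired with a home-living participant who shares the same age, race and 2019 comorbidity flags.

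If residents' risk of COVID-related hospitalization differs from that of otherwise similar people at home, the difference enters the primary comparison as if it were a drug effect. A larger sample does not remove this bias; it makes a false positive result more likely. The sponsor evidently saw the distinction, since it planned to collect a variable that expresses it, but the plan does not say what the variable is for.

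**Working it through.** **Would the plan bring the flag into the matching?**
- SAP 5.8.1.1 keeps covariates that are consistent across three iterations, then finalises the set from data, literature and clinician decision.
- Iteration 2 uses study participants only. If they are infused at home, the flag should be almost always negative there. A nearly constant covariate cannot show an association, so the rule would tend to drop it unless clinicians override it.
- The rematching loop in SAP 5.8.1.2 responds to imbalance in the matching covariates. A variable outside that list does not trigger it.

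**The plan's own figure.** Table 2 gives 940 in total for 25% against 16.25% (a 35% reduction), two-sided 5%, 90% power, with continuity correction.
- Uncorrected n per group = [1.960·√(2·0.20625·0.79375) + 1.282·√(0.25·0.75 + 0.1625·0.8375)]² / 0.0875² = 447.3.
- Corrected n = (447.3/4)·[1 + √(1 + 4/(447.3·0.0875))]² = 469.9, so 470 per group and 940 in total.

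The figure reproduces. This point disputes no sample size.

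**Size of the bias**

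Inputs:
- Home rate b = 15%, borrowed from the control rate in the SAP 4.4.2 fallback calculation.
- 1,000 per group (SAP 4.4.2 fallback) and 7,500 per group (target).
- Assumed, not in the documents: a share f of matched controls are facility residents; their risk is m times the home risk after matching; no residents among the treated; no drug effect.

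Formulas:
- Control rate c = b·(1 − f + f·m).
- Spurious relative reduction = 1 − b/c. This does not depend on b.
- Rejection probability of the two-sided 5% pooled two-proportion test = Φ((d − 1.96·se₀)/se₁) + Φ((−d − 1.96·se₀)/se₁), with d = c − b, se₀ the pooled and se₁ the unpooled standard error.

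Example, f = 10%, m = 2:
- c = 0.15·(0.90 + 0.20) = 0.165, and 1 − 0.15/0.165 = 9.1%.
- At 1,000 per group, d = 0.015 and both standard errors are about 0.0163, so the rejection probability is about 0.15.

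| f | m | Control rate | Spurious reduction | Rejects at 1,000 per group | Rejects at 7,500 per group |
|---|---|---|---|---|---|
| 2% | 1.5 | 15.15% | 1.0% | 5.1% | 5.8% |
| 5% | 2 | 15.75% | 4.8% | 7.5% | 24.7% |
| 10% | 2 | 16.5% | 9.1% | 15.1% | 71.3% |
| 10% | 3 | 18.0% | 16.7% | 43.9% | 99.9% |

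Opposite direction, f = 10%, m = 0.5: c = 0.15·(0.90 + 0.05) = 14.25%, and 15/14.25 = 1.053. An ineffective drug would then appear to raise hospitalization by about 5%.

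**The case against.** The best defence is that the covariate set is not final. The flag is a listed potential covariate, Table A5 is marked as subject to change, and the table shells are not exhaustive: SAP 5.8.1.1 names state or county as a risk factor, yet A5, A8 and A11 have no row for either. This stands to the extent that a missing row does not prove exclusion. It does not show that the flag will be used, and the consistency rule works against it.

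Table A4.2 would show an imbalance after matching. That also stands, if the data are complete, but the plan attaches no consequence to it.

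Age, dual status and Elixhauser conditions such as paralysis, neurological disorders and weight loss carry part of the difference. This is fair, and is why m above is the ratio remaining after matching. None of them records residence, and the comorbidities date from 2019.

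The E-value in SAP 5.8.2 is aimed at unmeasured confounding; this variable is to be collected.

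A reader might infer that residents are a higher-risk group with no treated counterpart at all. The documents do not support that. They give no rate by residence, no criterion bars residents from enrolling, and the flag is collected for participants too. That counterparts are few is an inference from home infusion and the flag's own wording.

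**Conclusion.** The gap is real: the plan has no living-at-home requirement for controls, and no commitment to use the flag in forming or checking the matched groups. Facility residents can enter the matched controls with few or no treated counterparts.

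The direction of any bias depends on their remaining risk: toward the drug if it is higher, against it if lower. Under the assumed ranges above (f from 2% to 10%, m from 1.5 to 3) the spurious reduction is about 1% to 17%. The lower end is negligible and the upper end is an assumed extreme, not an estimate. The documents cannot place the trial within that range. What justifies a change is that a planned variable can largely close the gap at low cost.

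**What to change.** In the Table 3 efficacy populations, exclude persons in both groups whose nursing-facility flag is positive as of the infusion or synthetic index date. Alternatively, match exactly on the flag and show it in A8.2 and A11.2. Keep every treated participant in the safety population.

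Define the flag only from claims or EMR records dated before the index date, after claims run-out. Do not fill it from BCRT: that source records inpatient admissions, so it could flag hospitalized controls preferentially and make the exclusion depend on the outcome.

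State how missing flags are handled, report the number excluded per group, and repeat the primary analysis with an alternative pre-index look-back. If exclusion is chosen, the flag is constant in the balance tables, so the exclusion counts are the useful report.

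Cost: a slightly smaller control pool, a wait for claims run-out, and some remaining misclassification of residence. The planned sample size does not change.

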4.4 Metrics and Variables

The primary outcome of interest is COVID-related hospitalization rate in study participants and matched controls. We list all potential covariates in two phases. Phase I covers historical data and Phase II includes post COVID-19 diagnosis information. Phase I historical data will be collected for both study participants and matched controls. Phase II post-COVID 19 diagnosis data has two parts: data elements to be collected for both study participants and matched controls (Phase II.A), and data elements to be collected for only study participants (Phase II.B).

Phase I - Historical data: Study participants and matched controls:

1. COVID-19-related information:

- Symptomatic or asymptomatic during COVID-19 test
- Number of COVID-19 cases per 10,000 people in the county of residence during COVID-19 test (if available)
- Number of COVID-19 deaths per 10,000 people in the county of residence during COVID-19 test (if available)

2. Demographic:

- Age as of 2020
- ZIP code of residence (may or may not be used for identifying matched controls)
- Urbanization of residence in a zip code level (urban, suburban, rural)
- Region/State of residence
- Race
- Gender
- Flag determining whether a patient resides in a nursing facility (or has been staying in a nursing facility currently) – determining patient does not live at home

3. Insurance:

- Line of business (should be mostly Medicare)
- Dual-eligibility status
- Continuous member enrollment in 2019
- Continuous member enrollment in 2020

3. Comorbidities in 2019:

- History of chronic kidney disease
- History of diabetes
- History of immunosuppressive disease
- History of cardiovascular disease
- History of hypertension
- History of chronic obstructive pulmonary disease/other chronic respiratory disease

- Elixhauser score for readmission
- Historical flag for all other associated comorbidities used in computing Elixhauser score (i.e., 29 categories like kidney disease, cancer etc.)

4. Immunosuppressive treatment

- History of receiving immunosuppressive treatment (6 months prior to date of COVID diagnosis)

Phase II.A: Post COVID-19 diagnosis data: Study participants and Matched controls

- Date of COVID-19 diagnosis test
- Type of COVID-19 diagnosis test (e.g., PCR, Antigen)
- Hospital admission date (if patient is hospitalized)
- Type of hospital admission (measuring level of trauma) (if available)
 - Through ER (if any)
 - With ICU transfer (if any)
 - With ventilation (if any)

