4.2 Data Collection

The data sources for study participants and the pool of potential controls are not all the same because we don't enroll matched controls in this study. To make sure both groups are symptomatic, we will use Optum electronic medical record (EMR) data to select symptomatic COVID-19 cases as candidates of control, while this information for study participants comes from ProtectWell symptoms data. We summarize the data sources for study participants and matched controls in Table 1.

For enrolled participants, tracked data collection begins from first report of symptoms via ProtectWell. The data collection timepoints are:

1. First report of symptoms
2. COVID-19 test result (positive – moves forward; negative – resets the experience)
3. Date of receipt of Bamlanivimab (LY3819253) via infusion (Day 1)
4. Day 1 infusion (pre, during, post) collection of CRF data (participant vitals/health information and any events experienced)
5. Day 1 post-infusion baseline wellness check through Day 28 final wellness check
6. Any point during Day 1 post-infusion baseline through Day 28 where wellness check indicates participant is feeling worse
7. Point from participant marking feeling worse through action taken (live daily check-in via clinical support, recommendation to seek medical care and/or requiring hospitalization)

Regarding the timeline, the overall duration for enrolled participants is up to 6 months with symptom tracking only. Once an enrolled participant becomes a study participant after reporting symptoms, it is up to 38 days (28 days of active participation after receipt of infusion on Day 1 and up to 10 days from report of symptoms to receive infusion). For matched controls, the active insurance coverage after date of symptoms onset should be up to 38 days. We require matched controls to remain enrolled in utilized data sources to assure data availability. Similar to enrolled participants, matched controls may die after the synthetic date of treatment.

Commented [WWY1]: Would suggest to add A figure to illustrate study design, including screening and treatment time point and assessment period

Commented [JAT2R1]: Thanks for the suggestion. I added a sentence directing the audience to Figures 2 and 3 on the screening process and timeline.

Table 1. Main data sources of study participants and the potential pool of controls.

Study population	Data name	Data description

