4.4.2 Patient Groups

Before analysis there are two study populations – study participants and the pool of potential controls. For study participants, we plan to enroll aged 65 and older, who are deemed high risk per the emergency use authorization, if contracting COVID-19. For the pool of potential controls, we plan to utilize UHC members who have Optum EMR data to confirm presence of symptoms during COVID test as well as having continuous enrollment to access to their claims and prospective hospitalization and death data. If applicable, non-UHC members or UHC members who did not seek care at OptumCare facilities may be used as members of the control population based on EMR review and matching to enrolled participants.

During analysis (i.e., after matching), there will be two study populations – study participants after matching and matched controls. Note that the size of study participants after matching may be smaller than the size of original study participants if a matched control can't be identified.

The targeted number of enrolled participants for tracking for symptoms is 500,000, and the targeted number of study participants who are COVID-19 positive and consent to receive Bamlanivimab (LY3819253) is 7,500. Figure 2 illustrates the process to identify study participants. Regarding controls, we set the case:control ratio at 1:1 and plan to identify 7,500 matched controls which is the same as number targeted for study participants.

Given the current enrollment speed (as of March 9, 2021) and the decreasing COVID-19 hospitalization rate across the US, we may not achieve the target number of study participants, 7,500. However, according to the power analysis in Section 4.3, it is sufficient to have 1,000 study participants with another 1,000 matched controls to detect a 33% decrease in the hospitalization rate (i.e., from 15% to 10%) with power 0.8 and level 0.05.

Commented [JAT7]: Remove as treatment is allowed in this situation per the EUA.

Commented [JAT8]: Remove prior vaccination from exclusion criteria as this is not required per the EUA.

Commented [WWY9]: Should we replace continuous member enrollment?

Commented [WWY10]: Given current enrollment speed, it will be helpful to show what is the minimal sample size for Bam treated group required for the primary objective analysis.

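### Controls must stay enrolled after the index date while participants are censored, and the plan does not say that death is not a break in enrollment

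*SAP*

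**What the plan says.** **Enrollment after index, controls.** SAP 4.2 states: "We require matched controls to remain enrolled in utilized data sources to assure data availability". It adds that "the active insurance coverage after date of symptoms onset should be up to 38 days", which matches the 10 days allowed from symptoms to infusion plus 28 days of follow-up. Protocol 4.2 has the same rule, tied to the UHC plan. In both documents the next sentence allows deaths: "Similar to enrolled participants, matched controls may die after the synthetic date of treatment".

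**Control pool.** SAP 4.4.2 plans to use UHC members with EMR data and "having continuous enrollment to access to their claims and prospective hospitalization and death data". It sets no matching condition for participants. The eligibility criteria in SAP 4.4.1 do not mention enrollment.

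**The 2021 variable.** SAP 4.7 files "Continuous member enrollment in 2021 (up to available months") under Phase I, the historical data. The corresponding list in protocol 4.4 stops at "Continuous member enrollment in 2020". The SAP introduces the whole list with "We list all potential covariates in two phases".

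**Timing.** SAP 4.4.2 speaks of accrual still running: "Given the current enrollment speed (as of March 9, 2021"). SAP 5.8.1.2 places matching after treatment enrollment and the 28-day period.

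**Censoring and death.** SAP 4.5 censors people without an event at Day 28 or, for study participants only, at an earlier loss to follow-up. SAP 4.7 (Phase II.A) collects a death date in both groups, and Day 28 mortality is the exploratory objective (SAP 3.2 and 5.9).

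**The concern.** Whether someone stays enrolled for up to 38 days after symptom onset is known only after follow-up has begun. Choosing controls on it conditions the comparison group on a post-index event. Participants face no such condition: if one is lost, the days already observed count and the person is censored. A control who leaves the plan on, say, Day 12 is either never selected or has no analysis rule.

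The 2021 variable adds to the problem. It is labelled historical but has no closing date, and it will be filled in after follow-up has ended. For an index date in 2021, the available months can include the follow-up period and later months. The value can also change with the data cut, and SAP 5.13 plans a primary analysis once the first 1,000 participants have Day 28 data.

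What is at stake depends on how death is coded. A member who dies also stops being a member. If the enrollment query treats that as a break, controls who die drop out, and those admitted before death take primary events with them.

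**Working it through.** **1. The plan's own figure.** SAP 4.4.2 calls 1,000 per group sufficient for 15% vs 10% at power 0.8, two-sided 5%. Without continuity correction:

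n per group = [1.960·√(2 × 0.125 × 0.875) + 0.842·√(0.15 × 0.85 + 0.10 × 0.90)]² / 0.05² = 686 after rounding up (726 with the correction).

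At 1,000 per group the power is 0.92. The statement is correct and conservative. No stated sample size depends on the enrollment variable.

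**2. Rules side by side.**

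| Event after index | Participants | Matched controls |
|---|---|---|
| Leaves data source alive before Day 28 | Censored at that date (SAP 4.5) | Must remain enrolled (SAP 4.2); no censoring rule |
| Dies before Day 28 | Allowed | Allowed (SAP 4.2); not stated whether this breaks enrollment |
| End of 2021 enrollment window | Not stated | Not stated |

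The first row is an asymmetry in the text as written. The other two rows are gaps.

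**3. Conditional illustration: decedents fail the requirement, controls only.** The rates 15% and 10% and 1,000 per group come from SAP 4.4.2. The documents give neither control mortality m nor the share h of deaths preceded by a COVID-19 admission. The assumed ranges are m = 1-3% and h = 80-90%.

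Observed control rate = (0.15 − m·h) / (1 − m); observed risk ratio = 0.10 / that rate.

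| m | h | Control rate | Risk ratio | Power at 1,000 per group |
|---|---|---|---|---|
| none dropped | – | 15.0% | 0.67 | 0.92 |
| 1% | 80% | 0.142/0.99 = 14.3% | 0.70 | 0.84 |
| 1% | 90% | 0.141/0.99 = 14.2% | 0.70 | 0.83 |
| 3% | 80% | 0.126/0.97 = 13.0% | 0.77 | 0.55 |
| 3% | 90% | 0.123/0.97 = 12.7% | 0.79 | 0.47 |

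The shift is toward 1, against the drug.

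**4. Same coding in both groups.** Assume treated mortality is two thirds of m, in line with 10% vs 15%. At m = 3%, h = 90%, the treated rate is (0.10 − 0.02 × 0.9)/0.98 = 8.4% and the risk ratio is 0.0837/0.1268 = 0.66. Over the whole range the risk ratio is 0.66 and the power 0.88-0.91. The primary comparison hardly changes.

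**5. Non-fatal disenrollment.** If a share d of controls leaves alive and their admission risk is r, excluding them gives (0.15 − d·r)/(1 − d). With r = 0.15 this equals 0.15 and nothing changes. It falls if r is above 0.15 and rises if r is below. The documents give neither d nor r, so no size or direction can be stated. Over a window of at most 38 days d is probably small.

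**The case against.** The strongest case on the other side is that the plan has already dealt with death. The sentence allowing controls to die follows directly on the stay-enrolled requirement and reads naturally as qualifying it. Death dates are collected in both groups, and SAP 4.4.2 ties continuous enrollment to having death data. The 2021 item sits in a list of potential covariates, does not appear among the covariates in mock Tables A5, A8 and A11, and may be no more than a look-back extension from January 2021 to index. It is listed for both groups, and SAP 5.1.1 restricts the analysis populations to UHC members, so a controls-only effect is not established.

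Most of this stands. A reader might infer that the 2021 item is an entry criterion that removes deaths and severe cases and leaves the mortality objective empty. The documents do not support that. The item is a potential covariate, control deaths are expressly allowed, and nothing says a hospitalized survivor loses coverage. Nor is the lowest power in the table, 0.47, a forecast. It needs decedents to be dropped, from controls only, at 3% mortality with 90% of deaths after admission, and none of these comes from the documents.

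The objection leaves the stay-enrolled requirement itself untouched. It is stated as a requirement, it applies after index, and it is stated for controls only. Calling the 2021 variable historical does not give it a closing date.

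**Conclusion.** The point holds as a design flaw in follow-up and selection: controls are conditioned on later enrollment while participants are censored, and control disenrollment before Day 28 has no rule. That rests on the text alone.

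The size is uncertain and may be small. The shift from 0.67 to about 0.70-0.79 applies only if death is coded as loss of enrollment, only among controls, and under the assumed mortality and admission shares. If deaths are kept, as the documents most naturally intend, what remains is non-fatal disenrollment, which is unquantified. If both groups are treated alike, the primary risk ratio barely moves. The change should still be made, because a stated rule selects controls on a post-index event and the correction is nearly free before outcome data are accessed.

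**What to change.** - **SAP 4.7:** end the 2021 enrollment variable at the COVID-19 diagnosis date and apply it identically to participants and controls.
- **SAP 4.2 and 4.4.2, protocol 4.2:** remove the requirement that controls remain enrolled. State that enrollment after index is neither a selection nor a matching condition.
- **SAP 4.5:** follow both groups to COVID-19 hospitalization, death, disenrollment or Day 28, whichever comes first, under one rule. State that death does not count as disenrollment.
- **SAP 5.8.1.3, binary endpoint:** say how people who disenroll alive before Day 28 without an event are handled, do it the same way in both groups, and report their number by group.

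The cost is wording in the two documents and a date cut in the enrollment query. The small downside is that a few controls with incomplete follow-up are kept instead of dropped.
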